Date: June 13th 2019

Comparison of Gastric Volume After 6-hour and 8-hour Fasting in Patient Scheduled for Elective Surgery

[name], [name], [name]

Department of Anesthesiology and Intensive Therapy

Faculty of Medicine, University of Indonesia- RSUPN [name]

[name]

Background

The incidence of perioperative aspiration associates with significant morbidity and mortality for patients who will undergo surgery, especially in the length of hospitalizations and use of mechanical ventilation.¹ Perioperative aspiration is an undesirable risk although the incidence is rare. The incidence of aspiration ranges from <0.1% to 19% depends on patient factors and factors of surgery performed.² Sedation and anesthesia reduce or even eliminates physiological reflexes that protect the risk of aspiration, such as *lower esophageal sphincter* muscle tone and upper airway reflex.³

One of the risk factors of aspiration is the amount and type of gastric content so that elective surgery patients will fast before the operation. ASA guideline recommends 8 hours of fasting after eating for patients who will undergo elective surgery.⁴ 8-hours fasting after consumption of fatty foods or fried foods are considered adequate by ASA guideline for the elective surgical patient.⁴ However, special conditions such as diabetes patients, critical patients, digestive disease, and other diseases cause variations in the duration of gastric emptying.^{2,4} The longer patients do the fasting increase the risk of dehydration, hypoglycemia, and other problems, especially in patients with metabolic disorders. RSCM recommends 6-hours of fasting before undergoing elective surgery to reduce the period of prolonged fasting. Moreover, the types of food consumed in Indonesia have a lower fat content compared to ASA guidelines.

Ultrasound examination is an invasive examination and easy to administer performed which can show the volume of the hull in *real-time* to predict aspiration risk. Gastric volume resulting in an increased risk of aspiration remains controversial, but healthy patients who do fasting often have a residual gastric volume of about 1.5 ml/kg without an increased risk of aspiration.^{2,4}

Until now, several studies have stated that ultrasound examination can predict gastric volume. This examination is useful for assessing the patient who in an emergency condition with an unclear fasting condition that requires medical treatment soon. A study assessing gastric contents in fasting patients using ultrasound has not been done in Indonesia. Ultrasound of gastric contents has become an option in many countries such as Sweden, and Canada to assess the risk of perioperative aspiration.

Research Problems

Prolonged fasting can negatively affect the patient, especially the patient with a high risk of anesthesia. Currently, in RSCM, 6 hours of fasting is considered sufficient as preparation for elective surgery. There are differences from the ASA guidelines that state recommendations for 6-hours fasting after snacks and 8-hours fasting after solid foods. This research aims to analyze the difference in gastric volume after 6-hours of fasting compared with 8-hour fasting in patients undergoing elective surgery.

Research purposes

This study aims to compare gastric volume in fasting patients as preparation for elective surgery. Prolonged fasting has a negative impact on the patient's condition, especially patients with risk factors such as sepsis, diabetes, and various other conditions. If there is no significant difference in gastric volume after 8 hours of fasting compared to gastric volume after 6 h of fasting, then a 6-hour fasting period may be considered to reduce the risk of aspiration in the patient who will undergo elective surgery.

Research Methods

Research design

This is a cohort study of patients undergoing non-digestive elective surgery. This research was conducted in the hospital ward RSUPN dr. Cipto Mangunkusumo from January to February 2019. The estimated number of samples with an estimated *drop out* of 10% are 35 subjects. Sampling is done after obtaining approval from the Ethics Committee of the Faculty of Medicine, University of Indonesia.

Inclusion and Exclusion Criteria

The inclusion criteria were patients aged 18-60 years, ASA 1-2 who would undergo non-digestive elective surgery in RSCM with a body mass index between 20-30 kg/m². Exclusion criteria were a patient who is not willing to enter the study, patients with diabetes mellitus, pregnancy, abdominal distension, intestinal motility disorders, history of dyspepsia, or patients who do not receive the standard RSCM diet and changes of the surgery schedule in which the patient is unable to do 8-hours fasting before surgery, the patient who has an emergency in the perioperative period and the patient was unable to consume the standard food provided.

Sampling technique

Samples were obtained consecutively. Subjects were recruited based on an elective operating schedule recorded at the RSCM one day before the procedure. Subjects who met the inclusion criteria and did not have exclusion criteria will be explained regarding the research procedure in the ward by researchers. A sign of consent to be included in the research will be written on the informed consent sheet if the subject is willing to take part in the research. If the subject cannot sign the informed consent sheet, the signature can be represented to the patient's main family.

Data collection techniques and variables to be measured

After the subjects agree to take part in the research, an initial examination will be carried out for obtaining subject demographic data, including age, weight and height, type surgery to be performed, and preoperative examinations. The subject will start 8 hours of fasting before the surgical planning time. Before fasting, the subjects were given standard food RSCM with standardized nutritional levels. Subjects were given 1 hour to consume the standard RSCM food. 6 hours after the standard meal is consumed, an ultrasound examination will be performed with the right lateral decubitus position to obtain ultrasound imaging of the antrum after 6 hours of fasting. After that, the subject continues fasting for up to 8 hours after consumption of solid food. Furthermore, an Ultrasound examination is performed using the same technique to obtain images of ultrasound imaging of the antrum after 8 hours of fasting. Imaging pictures are taken at the time relaxation of the antrum, between two contractions. The results of this imaging are stored and assessments of antrum craniocaudal (CC) and anteroposterior (AP) diameters were performed by research assistants who don't know when the image was taken. The volume of the stomach was calculated with the formula $GV = 27.0 + 14.6 \times CSA - 1.28 \times age$.

Statistical analysis

The data collected is processed using the Statistical Package for Social Scientist program (SPSS) version 23.0. Numerical data with normal distribution will be analyzed using the T-test

in pairs. If the data has an abnormal distribution, the data will be analyzed using the Wilcoxon test. The data obtained is the result of repeated examinations, so that the

analysis will be adjusted using the Bonferroni correction factor. Categorical data will be analyzed using the McNemar test. The results of data processing are displayed in tabular form. The CSA can be calculated with the formula $CSA = \frac{\pi \times CC \times AP}{4}$. The gaster volume was grouped into sufficient and insufficient with a border value of 1.5ml/kg.

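### A non-significant test of difference is the only stated ground for supporting a 6-hour fast, and it cannot show that 6 hours leaves no meaningfully greater gastric volume

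*Combined protocol and SAP*

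**What the plan says.** The Research purposes section links data to conclusion in one sentence. The condition is "If there is no significant difference in gastric volume after 8 hours of fasting compared to gastric volume after 6 h of fasting"; the consequence is "then a 6-hour fasting period may be considered". No other criterion for supporting 6 hours appears in the document.

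The Statistical analysis section then lists the methods:

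- For continuous volume: "Numerical data with normal distribution will be analyzed using the T-test", in its paired form, with the Wilcoxon test if the data are not normal.
- For multiplicity: "analysis will be adjusted using the Bonferroni correction factor". The number of comparisons is not given.
- For categories: "Categorical data will be analyzed using the McNemar test".
- For the cut-off: "The gaster volume was grouped into sufficient and insufficient with a border value of 1.5ml/kg".

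Research design gives the sample size, including dropout, as "of 10% are 35 subjects", and places the conduct of the study "from January to February 2019". The document itself is dated June 2019. It states no alpha, power, SD, effect size, margin or confidence interval.

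**The concern.** A paired test suits the stated aim of analysing the difference between the two times. The fault lies in what is concluded when that test is not significant. A p-value above the threshold says the data are compatible with no difference; it does not say they are incompatible with a difference that matters.

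Under this rule poor precision is rewarded. Fewer patients or noisier ultrasound measurements make the favourable reading more likely, and so does a stricter alpha if Bonferroni covers more than one test. Nothing in the plan limits the chance of accepting 6 hours when more volume remains at that time.

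The Background calls the volume that raises aspiration risk controversial and says the hospital already recommends 6 hours. A null result would therefore be taken as support for current practice when it may reflect only imprecision.

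**Working it through.** **What can be reproduced.** The 35 subjects cannot be rebuilt, because alpha, power, effect size and SD are absent. Only the dropout step can be checked: 31 / 0.90 = 34.4, rounded up to 35. So n = 31 evaluable pairs is used below.

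**Assumptions (not in the documents).** Paired t-test; two-sided alpha 0.05, or 0.025 if Bonferroni covers two tests; true 6-hour excess d in SDs of the paired difference.

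**Chance of a non-significant result.** This is the probability that a noncentral t with 30 df and noncentrality d√31 lies between −c and c. The critical value c is 2.042 at 0.05 and 2.360 at 0.025.

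| d | d√31 | alpha 0.05 | alpha 0.025 |
|---|---|---|---|
| 0.3 | 1.67 | 63% | 74% |
| 0.4 | 2.23 | 42% | 54% |
| 0.5 | 2.78 | 23% | 34% |
| 0.7 | 3.90 | 4% | 7% |

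The excess detectable with 80% power is 0.52 SD at 0.05 and 0.58 SD at 0.025.

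**Dependence on sample size.** At d = 0.4 and alpha 0.05, the favourable reading occurs in 60% of studies with 20 pairs, 42% with 31 and 2% with 100. The same true excess is thus more likely to be passed over in a smaller study.

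**Precision.** The 95% CI half-width is 2.042 / √31 = 0.37 SD. With an assumed SD of 20 mL that is about 7 mL; with 40 mL, about 15 mL.

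**The 1.5 ml/kg grouping.** Assume the exact McNemar test, with k patients above the cut-off at 6 hours and below it at 8, and none the other way. Then p = 2 × 0.5^k.

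- k = 5 (5/31 = 16%): p = 0.063, non-significant at 0.05.
- k = 6 (6/31 = 19%): p = 0.031, significant at 0.05 but not at 0.025.
- k = 7: p = 0.016, significant at both.

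So five patients could move across the plan's own cut-off, all in the unfavourable direction, and the result would still count as no significant difference.

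**The case against.** The strongest reply is that the plan claims little. It never says equivalent, non-inferior or safe; it says 6 hours may be considered, in a statement of purpose rather than a formal decision rule. That is fair as to tone, but the sentence is still the only stated route from data to conclusion.

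A second reply is that 1.5 ml/kg gives a clinical reference apart from the p-value, since the Background associates about that volume with fasting patients not at raised risk. But the cut-off classifies one volume at a time, no conclusion is attached to it, and McNemar is again a test of difference.

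Third, what could be missed may be modest. With 31 pairs, non-significance at 0.05 keeps the observed difference below 0.37 of the observed SD, so the upper 95% limit is below about 2 × 0.367 = 0.73 SD. That is about 15 mL if the SD is 20 mL and 29 mL if it is 40 mL. At an assumed 60 kg, these are 0.24 and 0.49 ml/kg, or 16% and 33% of 1.5 ml/kg. This might reassure, but it rests on assumed SDs and weight, and it argues from a confidence limit that the plan does not promise to report.

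Two cautions stand. With two scans per patient there is only one pairwise comparison of volume, so Bonferroni changes nothing unless a second test is counted; the 0.025 figures depend on that. The McNemar example takes all discordance in one direction, and the documents give no expected proportions.

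**Conclusion.** The concern holds and must be fixed. Applied as written, the plan can turn imprecision into support for 6 hours. This follows from the logic of the criterion and does not depend on any assumed number.

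The size is illustrative. For true excesses of 0.3 to 0.5 SD, the favourable reading arises in 63% down to 23% of studies with 31 pairs at two-sided 0.05, and in 74% down to 34% if Bonferroni covers two tests. The plan would usually detect a large excess of 0.7 SD. Whether the smaller excesses matter clinically cannot be judged, because the documents give neither an SD nor a margin.

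**What to change.** Delete the inference from non-significance. Report the paired 6-hour minus 8-hour difference in mL and mL/kg with a two-sided 95% CI: the mean difference, or the Hodges-Lehmann estimate where the Wilcoxon test is used. Conclude only what the interval excludes. Beside McNemar, report how many patients crossed 1.5 ml/kg in each direction. The same sentence also speaks of lowering aspiration risk; showing that 6 hours is no worse on volume would not support that, so it needs rewording too.

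If the results have not been seen, the investigators could instead fix and justify a margin, claim that 6 hours leaves no meaningfully greater volume only if the upper 95% limit lies below it, and otherwise report an inconclusive result. Given conduct in January to February 2019 and a June 2019 document, this option may already be closed.

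The main change costs some wording and an interval from data already planned. The price is that the study may well be inconclusive. With 31 pairs and no true difference, the margin rule succeeds in about 37% of studies at a 0.3 SD margin and 77% at 0.5 SD. For 80%, the normal approximation ((1.960 + 0.842) / margin)² gives 88 and 32 evaluable pairs; the exact t calculation gives 90 and 34.

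### A non-significant difference between 6 h and 8 h is enough to support the 6-hour fast; the plan's own 1.5 ml/kg grouping has no stated role in that conclusion

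*Combined protocol and SAP*

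**What the plan says.** The aim under Research Problems is relative: "This research aims to analyze the difference in gastric volume after 6-hours of fasting compared with 8-hour fasting". Research purposes turns it into a rule. The condition is "If there is no significant difference in gastric volume after 8 hours of fasting compared to gastric volume after 6 h of fasting", and the consequence is "then a 6-hour fasting period may be considered to reduce the risk of aspiration in the patient who will undergo elective surgery". No other sentence links a result to a conclusion.

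The plan has one absolute standard, under Statistical analysis: "The gaster volume was grouped into sufficient and insufficient with a border value of 1.5ml/kg". Its basis is in Background: "healthy patients who do fasting often have a residual gastric volume of about 1.5 ml/kg without an increased risk of aspiration". The same sentence in Background calls the volume at which aspiration risk rises controversial.

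The planned tests are a paired t-test ("Numerical data with normal distribution will be analyzed using the T-test"), the Wilcoxon test if the data are not normal, and McNemar ("Categorical data will be analyzed using the McNemar test"). The plan adds that the "analysis will be adjusted using the Bonferroni correction factor", without giving alpha or the number of tests. It names no primary analysis.

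**The concern.** The consequence in the rule is about aspiration risk, but its condition is only that 6 h looks like 8 h. Similarity between two times does not show that the stomach is acceptably empty at either. The study will hold the information that bears on this, namely how many patients exceed 1.5 ml/kg at 6 h, yet no text gives that count any weight.

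This is a separate matter from whether non-significance can establish similarity. An equivalence margin on the difference, even if met convincingly, would still say nothing about the level at 6 h.

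At stake is a published statement on aspiration risk that the study's own grouped data might contradict. The converse problem is a small but significant difference, with every patient below the border, that the plan gives no way to interpret.

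**Working it through.** **1. Number of pairs.** Research design gives 35 subjects including 10% drop-out. The 35 cannot be derived, because no alpha, power, effect size or SD is stated. Only the drop-out step can be checked: 31/0.9 = 34.4 and 31 × 1.1 = 34.1, both rounding up to 35. With 30 the results are 34 and 33; with 32 both are 36. About 31 evaluable pairs are implied.

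**2. What each test can see.**

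| Planned analysis | Uses | Tests 6 h against the border? |
|---|---|---|
| Paired t-test or Wilcoxon | Within-patient differences, 6 h v 8 h | No |
| McNemar | Only patients who change group between the two times | No |

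If the mean volumes are truly equal, the paired t-test at 5% is non-significant in 95% of trials, whatever the common level of volume.

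**3. Illustration: many above the border at both times.** Assume that the same 8 of 31 patients exceed 1.5 ml/kg at both times and that volumes do not change.
- Mean paired difference = 0. Discordant pairs are 0 and 0, so McNemar p = 1 and the rule supports 6 h.
- Share above the border at 6 h = 8/31 = 25.8%; exact (Clopper-Pearson) 95% CI 11.9% to 44.6%.

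The 8 is an assumption, since the documents give no expected share.

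**4. Illustration: small difference, all below the border.** Assume a mean fall of 6 mL between the scans. At an assumed weight of 60 kg this is 6/60 = 0.1 ml/kg, against a border of 1.5 × 60 = 90 mL. The power of the two-sided paired t-test comes from the noncentral t distribution with 30 degrees of freedom and noncentrality 6 × √31 / SD. The SD of the difference is not stated, so a range is shown. Alpha 0.025 represents Bonferroni over two tests, also assumed.

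| SD of difference (mL) | Noncentrality | Power, alpha 0.05 | Power, alpha 0.025 |
|---|---|---|---|
| 8 | 4.18 | 98% | 96% |
| 12 | 2.78 | 77% | 66% |
| 20 | 1.67 | 37% | 26% |
| 30 | 1.11 | 19% | 12% |

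A significant result of this kind ranges from likely to uncommon, depending on an SD that the plan does not give. If it occurs, the plan does not say what to conclude.

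**5. What the 6 h share could show with 31 patients.**
- 0/31 above: upper exact limit 1 − 0.025^(1/31) = 11.2% (two-sided 95%), or 1 − 0.05^(1/31) = 9.2% (one-sided 95%).
- 1/31 above: upper exact limit 16.7% (two-sided 95%).

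**The case against.** The strongest reply is that the study asks a relative question by design. Background reports that the guideline regards 8 h as adequate and that the hospital uses 6 h; comparing local practice with an accepted standard is legitimate. If the same patients exceed the border at both times, 6 h has performed no worse than that standard. The border is also not a validated pass or fail limit: Background calls the risk volume controversial, and the plan sets no failing share. This much stands. It is a reason to keep the 6 h v 8 h comparison as the aim and not to put an absolute gate ahead of it. It does not rescue the step from similarity to a statement about aspiration risk, because the plan measures volume at 8 h and chooses a border of its own.

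Two stronger readings are tempting, and the documents do not support them.
- A reader might infer that the rule rejects 6 h after a significant difference. It does not say so. It runs in one direction, is softly worded, and is silent on what follows a significant result. If it were read as referring to the McNemar comparison of the grouped volumes, the case with everyone below the border would give no significant result at all, although the first illustration would remain.
- A reader might infer that the measured volume and the border are never brought together. They are: weight is collected, the grouping is planned, and categorical data have a named test. The 6 h count would probably appear in a table. What is missing is its role in the conclusion.

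**Conclusion.** The point holds as a gap in interpretation, and closing it is a cheap improvement. A non-significant 6 h v 8 h difference is the only stated condition for a conclusion about aspiration risk. The 1.5 ml/kg grouping plays no part in that conclusion, and no planned test looks at 6 h on its own. The rule can support 6 h with about a quarter of patients above the border, as in the 8 of 31 illustration. It also leaves a small significant difference uninterpreted when all patients are below the border.

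The count of 8, the 6 mL fall, the 60 kg weight and the SDs are assumptions; the 31 pairs are inferred from 35 less drop-out. The logical gap depends on none of them. How often the second situation would arise depends heavily on the SD: 98% down to 19% at alpha 0.05 across the range shown. None of this indicates which fasting period is right, or that 1.5 ml/kg is the right border.

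**What to change.** Keep the 6 h v 8 h comparison as the stated aim. Amend the conclusion in Research purposes, and add matching text to Statistical analysis, so that the conclusion rests on two results:

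1. the paired 6 h v 8 h difference with its confidence interval;
2. the number and share of patients above 1.5 ml/kg at 6 h, and at 8 h, each with an exact 95% confidence interval.

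Limit any statement about aspiration risk to what the 6 h share and its upper limit support. Say that similarity to 8 h does not by itself show adequacy at 6 h, and that a significant mean difference does not by itself show inadequacy.

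**Cost.** Wording only, since the grouping is already planned and weight is collected. The claim becomes more modest: with about 31 patients, 0/31 excludes only shares above about 11%, and 1/31 only shares above about 17%. A formal maximum share judged on the upper limit is therefore a debatable choice at this size and is not required here. The document is dated June 2019 and gives January to February 2019 as the study period, so any acceptable share named now should be declared as set after data collection.

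### Does excluding patients with a perioperative emergency remove valid scan pairs and bias the 6-hour versus 8-hour comparison?

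*Combined protocol and SAP*

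**What the plan says.** The list in Inclusion and Exclusion Criteria contains "the patient who has an emergency in the perioperative period". It defines neither an emergency nor the limits of the perioperative period. The item before it is qualified: "changes of the surgery schedule in which the patient is unable to do 8-hours fasting before surgery". The item after it concerns patients who could not eat the standard meal.

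Under Data collection techniques and variables to be measured, the timing is: "The subject will start 8 hours of fasting before the surgical planning time". A scan follows at 6 hours, and then: "Furthermore, an Ultrasound examination is performed using the same technique to obtain images of ultrasound imaging of the antrum after 8 hours of fasting". No later study procedure is described. On the images, the plan says: "The results of this imaging are stored"; the antral diameters are then read by assistants who do not know when each image was taken.

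The Statistical analysis section compares the two times by paired t-test or Wilcoxon test and uses McNemar's test for categorical data. It adds: "The gaster volume was grouped into sufficient and insufficient with a border value of 1.5ml/kg". No analysis set is defined.

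**The concern.** The neighbouring exclusions are tied to the fast or the meal, and this one is not. Patients are recruited from the operating list the day before surgery, when a perioperative emergency cannot yet be known, so the item can act only after enrolment. The perioperative period ordinarily runs through and beyond surgery, by which time both outcomes have been measured. Read literally, the rule lets an event after the outcome decide who is analysed.

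If the event has nothing to do with stomach contents, a valid pair is lost and the cost is precision. If it does, removal depends on the outcome. The Background says: "One of the risk factors of aspiration is the amount and type of gastric content". Dropping a patient who aspirated could therefore remove a high volume. That would lower the mean volumes and the proportion above 1.5 ml/kg, and would pull the paired difference slightly towards zero. Under Research purposes, finding no significant difference is what would support the shorter fast, so the error would run in the reassuring direction.

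**Working it through.** **Setting the text side by side.**

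1. The fast begins 8 hours before planned surgery, so the whole fast lies in the immediate preoperative window. An emergency in that window can spoil the fast or prevent a scan, which gives the exclusion a natural role before the last measurement.
2. The items on either side both concern whether the meal and fast could be carried out. In that company the feasibility reading is the more natural one.
3. The study is set on the ward, and the 8-hour scan is the last contact described. No intraoperative or postoperative observation, adverse-event collection or aspiration outcome is planned. Removing a complete pair would need both the literal reading and a follow-up step that the plan does not contain.

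**Size if the literal reading were applied.**

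Inputs from the documents: 35 patients including 10% dropout (Research design). 35 × 0.9 = 31.5, taken as 31 pairs; in the other direction, 31/0.9 = 34.4, which rounds up to 35.

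Assumed inputs, because the documents give none: a content-related event rate after the 8-hour scan of 0.1% to 1%; a removed patient 2 SD above the mean at 6 hours; equal variances at the two times; a correlation ρ between scans of 0.8 to 0.5; two-sided 5% and 80% power.

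*Number of removals, binomial with n = 35:*

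| Rate | Expected | P(at least 1) | P(at least 2) |
|---|---|---|---|
| 0.1% | 0.035 | 1 − 0.999^35 = 3.4% | 0.06% |
| 1% | 0.35 | 1 − 0.99^35 = 29.7% | 4.8% |

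*Shift in the 6-hour mean after k removals:* 2k/(31 − k). For k = 1, 2/30 = 0.067 SD. For k = 2, 4/29 = 0.138 SD.

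*Shift in the paired difference, in SDs of the difference:* 2kr/(31 − k), where r = √((1 − ρ)/2) is the correlation of the 6-hour volume with the difference.

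| ρ | r | k = 1 | k = 2 |
|---|---|---|---|
| 0.8 | 0.316 | 0.021 | 0.044 |
| 0.5 | 0.500 | 0.033 | 0.069 |

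*Yardsticks.* With 31 pairs, the detectable paired effect is about 0.52 SD (noncentral t; 0.50 by normal approximation). The standard error of the mean difference is 1/√31 = 0.180 SD, so one removal moves the estimate by 0.021/0.180 = 0.12 to 0.033/0.180 = 0.19 standard errors.

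*Precision.* If 31 pairs gave 80% power, 30 would give 78.7% and 29 would give 77.3% (normal approximation).

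*Threshold at 1.5 ml/kg.* One removal could turn 1/31 (3.2%) into 0/30. McNemar's test is unchanged if that patient was above the threshold at both times, and loses one discordant pair if above at 6 hours only.

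**The case for a change.** The best case for acting is that the authors qualified the items on both sides and left this one open, that nothing says a patient with two scans is kept, and that a clarifying line would cost almost nothing. The single-time proportion above 1.5 ml/kg is also more fragile than the paired difference, since one patient can take it to zero. The event rate could be higher too: the Background cites aspiration incidence from below 0.1% up to 19%.

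Part of this stands. The wording is ambiguous, and the proportion is sensitive to a single patient. But the study's question is the difference between two times in the same patient, and that barely moves.

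The high end of the cited range depends on patient and surgical factors. This sample is ASA 1–2, elective and non-digestive, without diabetes, abdominal distension or motility disorder. A rate of 19% would mean 35 × 0.19 = 6.65 expected cases, more than the 35 − 31 = 4 losses the sample allows for, so it would not pass unnoticed. The Background also calls aspiration rare and its link with volume controversial, which weakens the bias route.

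Nor would rewording change conduct. The study ran "from January to February 2019" and the document is dated June 2019. A request to report later emergencies by reason would ask for information that the plan does not describe collecting.

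**Conclusion.** No change is needed. The exclusion is loosely worded, but its context supports reading it as an emergency that prevents the meal, the fast or a scan. An analyst running paired tests would ordinarily use every patient with both scans, and the stored images keep each pair available.

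Even on the literal reading, one content-related removal shifts the paired difference by 0.021 to 0.033 SD and two by at most 0.069 SD, against about 0.52 SD detectable. Two or more removals have a probability of 4.8% or less. These sizes rest on the assumed event rate, excess volume, correlation and power, none of which the documents give. The textual argument does not depend on them. No figure stated in the plan changes, and the 6-hour versus 8-hour comparison remains sound as written.

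### Blinding is stated only for the measurement step: the plan does not say who scans or selects the frame, and it sets no replicate or averaging rule

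*Combined protocol and SAP*

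**What the plan says.** All of the acquisition detail is in the section on data collection techniques and variables to be measured. The subject is scanned 6 hours after the standard meal in right lateral decubitus. Then: "After that, the subject continues fasting for up to 8 hours after consumption of solid food". At the second time point "an Ultrasound examination is performed using the same technique to obtain images of ultrasound imaging of the antrum after 8 hours of fasting". The capture rule is "Imaging pictures are taken at the time relaxation of the antrum, between two contractions". The images are stored, and the CC and AP assessments "were performed by research assistants who don't know when the image was taken".

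Volume comes from CSA and age through a fixed formula. The Statistical analysis section plans a paired t-test or Wilcoxon test, a McNemar test for categorical data, a Bonferroni adjustment, and a grouping of volume at 1.5 ml/kg. The Research design section gives the size: "The estimated number of samples with an estimated *drop out* of 10% are 35 subjects".

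The plan is silent on five things: who scans, whether that person is blinded to time, how many frames are kept per scan, how one relaxed frame is chosen over another, and whether readings are repeated or averaged.

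**The concern.** Blinded reading protects only the steps that come after the image exists. The order is fixed, 6 h then 8 h in the same person, so whoever holds the probe would ordinarily know which scan it is. If that person also decides which relaxed frame is kept, knowledge of time can enter before the blinded assistant sees anything. It could move the 6 h versus 8 h difference in either direction.

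Noise is a separate matter. Under Research purposes, the absence of a significant difference counts in favour of considering the 6-hour fast, and no margin is given. Under that rule, avoidable measurement error favours the conclusion that supports the shorter fast. Precision therefore matters more here than in a trial where noise only makes a positive claim harder to reach.

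**Working it through.** **Inputs from the plan.** 35 subjects including 10% dropout; GV = 27.0 + 14.6 × CSA − 1.28 × age; CSA = π × CC × AP / 4; two scans per subject.

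**Inputs not in the plan, so assumed.** Antral diameters; the share f of the single-frame paired-difference variance that is frame-to-frame noise; independent frame errors; two-sided alpha of 0.05 and 80% power. The number of comparisons behind the Bonferroni adjustment is not stated, so none is applied here.

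**1. The plan's own figure.** 31 / 0.90 = 34.4, rounded up to 35. Also 31 × 1.10 = 34.1, rounded up to 35. So 35 fits a base of 31 pairs. The 31 itself cannot be reproduced, because no difference, SD, alpha or power is given.

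**2. How a frame error reaches the endpoint.** Age is the same at both scans and cancels, so the difference in GV = 14.6 × the difference in CSA. For assumed diameters of 3.0 × 2.0 cm, adding 0.1 cm to both changes CSA by π/4 × (3.1 × 2.1 − 3.0 × 2.0) = 0.40 cm², and 14.6 × 0.40 is about 5.8 mL.

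| Assumed CC × AP (cm) | GV change, 0.1 cm on both | GV change, 0.2 cm on both |
|---|---|---|
| 2.0 × 1.5 | 4.1 mL | 8.5 mL |
| 3.0 × 2.0 | 5.8 mL | 11.9 mL |
| 3.5 × 2.5 | 7.0 mL | 14.2 mL |

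The same error carries into the 1.5 ml/kg grouping, and so into any McNemar test based on it.

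**3. Gain from averaging three frames at each scan.** Relative variance of the paired difference = (1 − f) + f/3. With 31 pairs and the assumed alpha and power, the detectable difference on one frame is 0.52 SD of the paired difference. With three frames it is 0.52 × √(relative variance), in the same single-frame units.

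| f (assumed) | Relative variance | Reduction | Detectable difference |
|---|---|---|---|
| 10% | 0.933 | 7% | 0.50 |
| 20% | 0.867 | 13% | 0.48 |
| 40% | 0.733 | 27% | 0.45 |
| 60% | 0.600 | 40% | 0.40 |

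**4. What averaging does not do.** Suppose there is no true difference and the selection shifts every retained frame at one time point by 0.25 single-frame SD. With 31 pairs and f = 50%, a paired t-test is significant 27% of the time with one frame. With three averaged frames the SD is multiplied by √0.667 = 0.816 and the shift is unchanged, so this rises to 38%. Averaging stills picked by an unblinded operator would make a shared shift easier to declare significant.

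**5. Reading load.** 35 × 2 × 1 = 70 images; 35 × 2 × 3 = 210. Each image needs CC and AP, so diameter measurements go from 140 to 420.

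**The case against.** The strongest reply is that the capture rule is itself the control. It fixes the antrum in its relaxed phase and so removes much of the variation that contraction would cause. Position and technique are also the same at both scans, and reading is blinded to time. This stands in part: the scope for selection is limited to choice among relaxed frames, and the plan gives nothing to show how large that residual is. The lower values of f may be the realistic ones.

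A reader might infer that a time-aware operator is documented as choosing the frame, and that a single unreplicated frame is planned. The text supports neither. The operator's knowledge is a sound inference from the fixed order, but it is not stated. The plan speaks of images and pictures in the plural, so the accurate statement is that no replicate count or averaging rule is specified. The baseline of 70 readings depends on the same unstated single-frame reading.

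Frames from one scan share operator, probe placement and patient position, so their errors may be correlated. The reductions above would then be too favourable.

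Finally, the document is dated 13 June 2019 and places the research in January to February 2019, so acquisition may already be complete. That limits what can be changed but does not close the gap in the written plan.

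**Conclusion.** The point holds as a minor design improvement. Stated blinding covers only the measurement of CC and AP; selection of the frame is unassigned and unprotected, and no averaging rule exists. The precision available from averaging three frames is a variance reduction of about 7% to 40% for f between 10% and 60%. This rests on assumed f and independent frame errors, neither of which the documents allow anyone to check.

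Two stronger conclusions are tempting and should not be drawn. One is that the 6 h versus 8 h comparison is biased: nothing in the documents shows a shift or its direction. The other is that averaging would cure selection bias: it would not, as step 4 of the working shows. Bias falls only if selection moves to readers who do not know the time. Even then it is reduced and not abolished, because the operator still controls probe plane and timing.

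**What to change.** State who performs the scans, whether that person knows the time point, and how many images are kept. At each scan store a clip, or all consecutive between-contraction frames under a fixed rule, and not stills picked by the operator. Have the existing time-blinded assistants select three relaxed frames, and use their mean CC and mean AP to compute CSA. Write the selection and averaging rule into the plan.

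This needs no extra scan, patient or second operator. The cost is reading time: about 210 image readings in place of 70 if one frame per scan was intended, plus the time to select frames from clips. The documents give no timings from which to cost this.

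If scanning is finished, report who scanned and how frames were chosen. Where several images per scan were stored, have the blinded assistants read and average them, and state that selection at capture was not blinded if that was so.
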